4 STUDY DESIGN

4.1 OVERALL DESIGN

This phase 2 cluster-randomized parallel groups trial will test the efficacy of the MASLIHAT intervention model on reducing risky drug, alcohol, and sexual behaviors among male Tajik labor migrants who inject drugs while working in Moscow in comparison with a control condition. This study will be conducted at the Moscow satellite site of PRIZMA Research and Training Center directed by [name]. We include only men because few Tajik labor migrants are women, and moreover injection drug use among Tajik women is rare. However, the intervention presumably will benefit the female sex partners of participants when the men return to Tajikistan. Recruitment will be conducted by outreach at twelve distinct sites, including diaspora organizations, bazaars, and worksites.

We will use cluster randomization, with each recruitment site being randomized to one arm of the study. The Tajik Diaspora Union, under the leadership of [name] (consultant), will assist with referrals. In both study arms, the recruited men (index participants) will be required to recruit two eligible MWID peers for interviews prior to being interviewed themselves. After peer-recruited network members are enrolled and interviewed, the index participant will participate in the MASLIHAT training as peer educators or the control group activities depending on their recruitment site. All participants

and network members will then be followed and re-interviewed at 3-month intervals for one year to assess changes in risky drug, alcohol, and sexual behaviors due to intervention participation and through diffusion to network members. We will also collect data from voluntary HIV and HCV testing conducted at 6 months (HCV) and at 12 months (HIV and HCV) post-intervention.

In the MASLIHAT intervention, we will train Tajik migrant MWID as peer educators who will deliver the intervention to their network members both during the five-week training and after completion. We will assess changes in drug, alcohol, and sexual risk behavior at 3, 6, 9 and 12 months post-intervention. **We hypothesize that the MASLIHAT intervention participants and their network members will experience a greater reduction in risk behavior compared to those in the control condition.**

We will examine mechanisms of behavior change among MASLIHAT participants, including purported mediators and potential moderators. We will assess changes in HIV knowledge, risk awareness, prevention self-efficacy, psychosocial well-being, and behavioral norms among participants and network members, and test associations with injection drug use (IDU) social network interactions and mediation of behavior change outcomes. **We hypothesize that the MASLIHAT intervention will influence behavior of both peer educators and network members by increasing knowledge and awareness of HIV transmission risks, modifying behavioral norms, and improving self-efficacy.**

4.2 SCIENTIFIC RATIONALE FOR STUDY DESIGN

We will use a cluster-randomized design to prevent control group contamination due to the nature of the intervention. Because the intervention is designed to reach the participant's social network through peer education activities, individual randomization to condition is not feasible.

The Targeted Application of Network and Social Intervention on Health Assistance for Tajiks (TANSIHAT) program will serve as the control condition. TANSIHAT was adapted from the Healthy Lifestyles for Labor Migrants intervention designed by Drs. [name] and [name] to serve as a control condition in testing an HIV prevention model delivered to Tajik migrants. We expanded the program contents to include TB risk and prevention and organized it to be parallel to MASLIHAT in the number and length of sessions. This program provides relevant health information for Tajik migrant workers and encourages participants to share the information with other migrants, but it does not address HIV/STI risk and prevention, condom use, or drug use. It does address heavy alcohol use which will affect our ability to detect effects on drinking behavior.

4.3 JUSTIFICATION FOR INTERVENTION

MASLIHAT is a small-group, interactive intervention that relies on peer networks to reduce drug, alcohol, and sexual risk behaviors among temporary migrant workers who inject drugs. It is based on a successful evidence-based peer-education approach for people who inject drugs in the U.S. (SHIELD), and adapted for migrant workers. Migrants in the host country who are current or former MWID are trained as peer educators to promote positive HIV risk-reduction norms and behavioral change through role modeling and sharing what they learned during MASLIHAT training sessions with their at-risk network members, especially other MWID. MASLIHAT fits well with the prevention needs of Tajik MWID living in

diaspora: 1) It is delivered by migrants to migrants, and not dependent on support from a host national health care system that denies them access to services; 2) Using current and former MWID to recruit and teach other MWID can reach migrant drug-using populations that are hidden or hard-to-reach; 3) It addresses risk reduction at both the individual and network levels; and 4) It requires little resource investment to implement. Staff at existing diaspora service organizations or former peer educators can serve as facilitators, and its 5 sessions can be delivered at any location with sufficient meeting space, including socio-geographic “hot spots” where risky behavior occurs. Pilot testing showed excellent acceptability and very promising results on risk behavior reduction.

The minimum acceptable participation for evaluation is 80% of participants attend all 5 sessions and 90% of participants attend at least 4 sessions. In pilot testing, all participants successfully recruited the required 2 network members and 83% completed the entire sequence of 5 MASLIHAT sessions; none missed more than one session.

4.4 END-OF-STUDY DEFINITION

A participant is considered to have completed the study if he or she has completed the baseline assessment, at least 4 intervention sessions, and the 6-month and 12-month follow-up assessments, and baseline and 12-month HIV and HCV testing.

The end of the study is defined as completion of the 12-month follow-up assessment and HIV/HCV testing shown in the Schedule of Activities (SoA), **Section 1.3**.

5 STUDY POPULATION

Study participants will include 1) 5 participants for pilot testing of instruments, 2) 140 index participants who receive the MASLIHAT or TANSIHAT control intervention, and 3) 280 network members of intervention participants.

5.1 INCLUSION CRITERIA

Participants for pilot testing will be Tajik men who currently inject or formerly injected drugs and who have experience as a migrant worker in Russia.

To be eligible as an index participant (MASLIHAT peer educator or control group member), prospective participants must meet the following criteria:

1. Male Tajik migrant age 18 or older
2. Show evidence of recent injection drug use (track marks)
3. Intend to reside in Moscow for the next 12 months
4. Agree to attend 5 weekly intervention sessions at PRIZMA
5. Agree to recruit 2 Tajik MWID network members to participate in interviews

6. Give informed consent

To be eligible for participation, network members must meet the following criteria:

1. Male Tajik migrant age 18 or older
2. Injected drugs at least once in the last 30 days (verified by inspection of track marks)
3. Someone whom the index participant sees at least once a week
4. Intend to reside in Moscow for the next 12 months
5. Give informed consent

5.2 EXCLUSION CRITERIA

Index participants will be excluded from participation in this study if:

1. they do not successfully recruit 2 network members within the allotted time frame, or
2. they do not attend the first intervention session

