5.4 SCREEN FAILURES

Screen failures are defined as participants who consent to participate in this study but are not subsequently entered in the study. This may occur if an index participant does not successfully recruit two network members within the allotted time period, or he does not attend the first intervention session. An index participant who does not meet the criteria for participation in this trial (screen failure) because of meeting one or more exclusion criteria may be considered for rescreening if the second group for the cluster has not yet been filled. Only index participants who identified more than 2 potential network recruits during screening will be allowed to replace network recruits who failed screening. Rescreened participants will be assigned the same participant number as for the initial screening.

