6.3 MEASURES TO MINIMIZE BIAS: RANDOMIZATION AND BLINDING

The 12 recruitment sites will be pair matched and randomly assigned to a study arm. One of each pair will be assigned to MASLIHAT and the other to the control condition. [name] will create the matched pairs based on site characteristics, and randomization will be determined by the PI using a random number generator. A random number will be generated for each site, and within each matched pair, the site with the smaller number will be assigned to MASLIHAT. To minimize bias during recruitment, site assignments will be masked from project staff engaged in recruitment. The PI will inform the Moscow project coordinator of the site assignment as needed for group scheduling, after the first cohort of participants has been filled for the site. Participants will be informed of their assignment at the time of scheduling the group sessions. [name] will also have access to this information as needed, after recruitment activities are underway. Interviewers will be blinded to site assignment, and the same interview instrument will be used for MASLIHAT and control condition participants. Session facilitators, who may become aware of the recruitment sites from which participants originated, will be instructed during training not to reveal this information to interviewers. Intentional or unintentional breaking of the blind is to be reported to the PI.

The randomization codes will be kept in a password-protected file accessible to the PI, co-investigators, the project coordinator, and the data manager. When preparing data for analysis, the data manager will

blind code recruitment site and study arm. Masking will be removed for reporting interim results to the DSMB.

In addition, we will adopt a position of clinical equipoise. Intervention facilitators and interviewers will be informed that we are testing two different interventions, but neither is assumed to be superior to the other. Facilitators will be assigned to one or the other, while interviewers will be blinded to participant condition. Data collection will be conducted by interviewers who are not involved in intervention delivery. Interviews will be standardized using a computer-assisted instrument, and sensitive sections will be self-administered.

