7.2 PARTICIPANT DISCONTINUATION/WITHDRAWAL FROM THE STUDY

Participants are free to withdraw from participation in the study at any time.

The investigator will discontinue a participant from the study for the following reasons:

- Failing to attend the first group session
- Lost-to-follow up; unable to contact subject (see **Section 7.3, Lost to Follow-Up**)
- Any event or medical condition or situation occurs such that continued collection of follow-up study data would not be in the best interest of the participant

The reason for participant discontinuation or withdrawal from the study will be recorded on the Withdrawal Case Report Form (CRF). Subjects who sign the informed consent form but do not receive the study intervention may be replaced. Subjects who sign the informed consent form and receive the MASLIHAT or Control (Healthy Lifestyle) intervention and subsequently withdraw, or are discontinued from the study, will not be replaced.

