8 STUDY ASSESSMENTS AND PROCEDURES

8.1 ENDPOINT AND OTHER NON-SAFETY ASSESSMENTS

Eligibility pre-screening. Potential index and network participants will call the PRIZMA Research Center for preliminary screening. The project coordinator will explain the study requirements and schedule an appointment for the enrollment visit (index participant) or enrollment and baseline interview (network member).

Screening & Enrollment. Participant screening, enrollment, and informed consent will take place in a private room at the PRIZMA office. A trained interviewer will interview each potential subject for the intervention conditions or as network members to identify those who meet the criteria to participate. Injection drug use will be confirmed by the presence of injection marks (tracks), or if marks are not visible, asking the subject about the injection process using a series of questions designed to identify PWID. The interviewers will then explain the purpose and activities of the study to eligible subjects and obtain informed consent from those who indicate their willingness to participate. Contact information also will be collected from the enrollees for follow-up purposes and the participants will be given contact information for the study coordinator should they have further questions.

Index participants. Project staff will confirm the participant's willingness to recruit two other Tajik migrant MWID for interviewing. Participants will complete a brief social network survey to enumerate their IDU network, and they will be given two coupons to recruit network members who meet the study criteria for interviews. Coupons will be valid for 30 days. Index participants will return to complete the baseline interview after network participants have enrolled.

Network participants. Project staff will check the participant's recruitment coupon and confirm his relationship to the index person who recruited him before continuing to administer the baseline interview.

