Interviews: Intervention participants and network members will complete computer-assisted personal interviews (CAPI) at baseline (prior to first intervention session), and at 3, 6, 9, and 12 months post-intervention. All baseline and 12-month interviews will be conducted in a private room at the PRIZMA office; intermediate follow-up interviews may be conducted at the PRIZMA office or at a location selected by the subject. Trained interviewers will administer the 60 to 90-minute questionnaire, using a computer-assisted personal interview (CAPI) system (Qualtrics) to record responses. For the more sensitive questions such as sexual behavior and STIs, the interviewer will instruct the participant to enter his responses. The CAPI system will ensure proper administration of skip sequences. For quality control purposes, 20% of interviews will be randomly selected to be audiotaped, and half of these audiotapes will be reviewed by [name] or [name] for quality assurance. Using electronic data capture and requiring timely data uploads will allow the data manager to monitor research progress and conduct quality control checks. The questionnaires were developed and tested with members of the population using cognitive interviewing (CI).⁶² Translations were validated using "back translation" with a member of the study population.

Self-report Measures

Background measures. The baseline interview includes measures of basic sociodemographic variables (education, marital status, migration history, religion), community involvement/social activities, and health (general health, STIs). The follow-up interviews also collect self-reported STIs since last interview.

Outcome measures. Primary outcome measures are syringe sharing in the past 3 months, and vaginal or anal sex without a condom in the past 3 months. Other measures include syringe cleaning methods, and the Alcohol Use Disorder Identification Test (AUDIT)⁶³ to assess alcohol consumption and alcohol-related problems at each time point.

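### Index men who miss session 1 are removed after baseline and arm disclosure, so the analysed set is not the ITT set that Section 9.3 names, and 9.3 and 9.4.2 disagree

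*Combined protocol and SAP*

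**What the plan says.** Three sections remove an index man who misses session 1.

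- Section 5.2 excludes index participants if "they do not attend the first intervention session".
- Section 5.4 defines screen failures as men who consent but are not then entered, and gives as a cause that a man fails to recruit two network members "or he does not attend the first intervention session". He "may be considered for rescreening if the second group for the cluster has not yet been filled".
- Section 7.2 lists "Failing to attend the first group session" first among the reasons for which the investigator will discontinue a participant from the study. It adds: "Subjects who sign the informed consent form but do not receive the study intervention may be replaced".

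Two sections fix what has already happened to him.

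- Section 8.1: "Index participants will return to complete the baseline interview after network participants have enrolled". The interview is placed "at baseline (prior to first intervention session", and the schedule in 1.3 puts the interview at Day 1 and the first session at Day 7.
- Section 6.3: "Participants will be informed of their assignment at the time of scheduling the group sessions".

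Two sections define who is analysed. Section 9.3 includes all who complete the baseline interview and calls this intention to treat. Section 9.4.2 includes all who have at least one follow-up interview.

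**The concern.** A man can be interviewed at baseline, learn which programme he will get, decide not to come, and then leave the study altogether. That is an exclusion made on behaviour after assignment is known. The two programmes are openly different: MASLIHAT deals with HIV, sex and injecting, and the control does not address HIV, condom use or drug use (6.1.1). If willingness to attend differs between them and is related to risk behaviour, the arms are compared on attenders only. A report that followed 9.3 in name and 9.4.2 in practice would call that comparison ITT.

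**Working it through.** **Tracing one man through the plan.** He recruits two network members and completes the baseline interview (8.1). He is told his arm when sessions are scheduled (6.3). The text does not say which of these two comes first, but both precede session 1. He misses session 1, so he is excluded (5.2), counted as a screen failure (5.4), discontinued and replaceable (7.2). He has no follow-up interview.

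| Section | Condition | Is he in? |
|---|---|---|
| 9.3 | Baseline interview completed | Yes |
| 9.4.2 | At least one follow-up interview | No |

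Anyone else with baseline data only falls into the same gap, so the two sections disagree whether or not the attendance rule stays.

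**Possible size of bias.** The documents give no session-1 no-show rate. The nearest figure is in 5.5: up to 150 index men screened for 140 enrolled, a margin of 10 (10/150 = 6.7%) for all screening reasons together. For illustration only, suppose a fraction f is lost from one arm only, the whole-arm risk is p and the leavers' risk is r. The observed follow-up proportion then falls by f(r − p)/(1 − f).

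- p = 0.35, f = 5/75 = 0.0667: 1.1 points if r = 0.5; 2.5 points if r = 0.7.
- p = 0.50, r = 0.8: 1.6, 3.3 and 5.3 points for f = 0.05, 0.10 and 0.15.
- r = p: zero.

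These figures overstate the effect on the planned repeated-measures analysis, because the leaver's baseline record goes too. If his excess risk is the same at baseline and follow-up, the shift in change is zero.

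**Power if these men are kept.** First, the plan's own cluster sizes: 70 × 0.90/6 = 10.5, 140 × 0.85/6 = 19.8, and (63 + 119)/6 = 30.3. These match the 10, 20 and 30 per site in 9.2.

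I then used 6 sites per arm, ICC 0.05, two-sided alpha 0.01, design effect 1 + (m − 1) × 0.05, and a normal approximation for two proportions with pooled variance under the null. Effective size per arm is 60/1.45 = 41.4 at m = 10 and 180/2.45 = 73.5 at m = 30. For 0.35 v 0.05 this gives 81.6% (index men) and 98.3% (complete sample), consistent with the at-least-80% claim in 9.2 for condomless sex, although 9.2 does not state that figure for index men alone.

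If a fraction f of the MASLIHAT arm keeps the control risk, that arm's risk becomes 0.05 + f × 0.30, which is 0.065 at f = 0.05 and 0.08 at f = 0.10. For the complete sample, network members are assumed to be diluted equally.

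| 0.35 v 0.05 | f = 0 | f = 0.05 | f = 0.10 |
|---|---|---|---|
| Index men | 81.6% | 74.6–76.4% | 66.9–70.4% |
| Complete sample (m = 30) | 98.3% | 96.4% | 93.2% |

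In the index row, the lower figure holds m at 10; the upper lets m rise to 10.5 or 11 because the men are extra.

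With 12 sites, a t reference on 12 − 2 = 10 degrees of freedom (critical value 3.17) is stricter. Taking noncentral-t power with noncentrality equal to difference/SE, and either the pooled or the unpooled SE:

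- Complete sample, f = 0: 0.30/0.0660 = 4.55 to 0.30/0.0612 = 4.90, power 88–93%.
- Complete sample, f = 0.10: 0.27/0.0678 = 3.98 to 0.27/0.0640 = 4.22, power 77–82%.
- Index men, f = 0: 0.30/0.0879 = 3.41 to 0.30/0.0815 = 3.68, power 61–69%.

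**The case against.** The best defence is that the rule is deliberate. Section 5 counts 140 men who receive a programme, 5.5 closes each group after its first session, and 5.4 says a screen failure was never entered. On that reading 9.3 covers entered men only. It does not hold up: 9.3 sets one condition, the baseline interview, and 7.2 treats the same man as a participant being discontinued from the study. Closing a group to newcomers also does not require ending anyone's follow-up.

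Much else in the defence stands. The rule is identical in both arms, the programmes match in number and length of sessions, and men agree beforehand to attend (5.1). Sites are randomised and none is lost. Index men are 140 of 420.

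A reader might go further and infer any of the following, which the documents do not support:

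- *The effect estimate is biased, perhaps in favour of MASLIHAT.* No attendance difference by arm is given or implied.
- *Section 7.1 contradicts 7.2.* It does not. It covers men who leave the sessions but not the study, and shows only that later leavers are followed.
- *His network members are lost too.* Section 5.2 excludes index men only, and 9.3 would keep anyone with a baseline interview.
- *Rescreening corrupts the baseline.* Section 5.4 keeps the same participant number, and an interview taken before the missed session still meets the 8.1 definition. More detail would help, but this is not an error.

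**Conclusion.** The point holds as a matter of text. Sections 5.2, 5.4 and 7.2 select index men on attendance after the arm is disclosed. Section 9.3 names an ITT set that this rule does not deliver, and 9.4.2 uses a different set again. The conclusion rests on the order of events in 6.3 and 8.1 and on no numerical assumption.

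The size and direction of any bias are unknown. The shifts of 0 to 5.3 points shown above rest on assumed no-show rates confined to one arm and on assumed risks among leavers; they are not estimates for this trial. The documents' own screening margin suggests few men. This should be corrected because the inconsistency is certain and the remedy is cheap, not because a large distortion has been shown.

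**What to change.** 1. Delete session-1 attendance as a reason for exclusion or discontinuation from the study (5.2, 5.4, first bullet of 7.2). Groups may still close after session 1.
2. Follow and analyse by assigned arm every index man with a baseline interview, and his network members, as 7.1 already does for men who leave the sessions later.
3. Allow replacement only before the baseline interview and before disclosure of the arm.
4. Amend 9.4.2 so that a participant with baseline data only contributes that record to the repeated-measures model, in line with 9.3.
5. Report session-1 attendance by arm.

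If the sponsor keeps the rule, 9.3 must not call the set ITT, and the number and baseline characteristics of excluded men must be reported by arm. That option needs only wording and reporting, but it gives up the ITT comparison among index men.

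**Cost of the main option.** Assume 5% to 10% of 140 index men, so 7 to 14, each with two network members: 21 to 42 men. Four follow-ups each give 84 to 168 interviews. At the $20 stated in 5.5 this is $1,680 to $3,360, plus voluntary HCV testing at 6 months and HIV and HCV testing at 12 months. If the network members would be followed anyway, only 28 to 56 interviews ($560 to $1,120) are added. The other cost is the dilution shown in the working, which is greatest if index men are analysed alone; 9.4.2 plans that only when the interaction term has p < .10.
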